#### 1. ABSTRACT

90 patients aged 20-60 years who were diagnosed with partial supraspinatus tear and met the inclusion criteria of the study will be included in the study. Patients will be randomized into three groups: 30 patients in the first group who have 5 sessions of high-intensity laser, 30 patients in the second group who have 10 sessions of high-intensity laser, and 30 patients in the third group control group who have only exercises. It was planned to give 5 sessions of laser+exercise every other day to the the first group, 10 sessions of laser+exercise every other day to the second group, and only exercise program three days in a week to the control group. All groups will be evaluated with joint range of motion (ROM) (measurements including abduction, adduction, flexion, extension, internal and external rotation by goniometer according to neutral 0 position), visual analog scale (VAS), shoulder pain dissability index, quickdash, constant score at 0th month, 1st month, 3rd and 6th months.

#### 2. AIM and PURPOSE

Rotatorcuff lesions constitute 10% of the causes of shoulder pain. Supraspinatus tear is one of the common rotatorcuff lesions (1). It affects the quality of life negatively and causes loss of range of motion and muscle strength (2,3). It can be seen due to traumatic or degenerative causes. Its incidence increases with advanced age. While the incidence was reported as 4% in the population aged 40-60 years, this rate was reported to be 17-50% in the group over the age of 60 and 80% in the group over the age of 80 (3,4). Radiologically, classification is made as partial or full-thickness tears. Rotatorcuff tears can be treated conservatively or surgically (5). Although the risk of post-surgical rupture is reduced with new methods, the lack of desired tendon healing has led to the search for alternative applications such as biological augmentation (6) and high-intensity laser (7). The aim of

this study is to reveal the effectiveness of high-intensity laser therapy in patients with partial supraspinatus tear.

# PRİMARY PURPOSE

Demonstrating the efficacy of high-intensity laser therapy in patients with partial supraspinatus tears

#### SECONDARY PURPOSE

Comparison of two different applications of high-intensity laser with 5 sessions and 10 sessions in terms of

Protocol name/ version number /date: Efficacy of high-intensity laser therapy in patients with partial supraspinatus tears Versiyon no: 02 - Tarih: 02.12.2020

effectiveness in patients with partial supraspinatus tear

## **3. HYPOTHESIS OF THE STUDY**

H0: High-intensity laser therapy is ineffective in patients with partial supraspinatus tears.

H1: High-intensity laser therapy is effective in patients with partial supraspinatus tears.

#### 4. SELECTION OF POPULATION & PATIENTS TO BE RESEARCHED

Disease	Partial supraspinatus tear
Number of Patients & Characteristics	women Man Age 20-65 Healthy : Patient :90 Total : 90

Volunteers will be included in the study among the patients who applied to the FTR outpatient clinic and were diagnosed with a partial supraspinatus tear of the shoulder.

Inclusion Criteria:

\*age between 20-65 years

\*Patients with VAS>4 pain in the shoulder for at least 3 months

\*Patients with at least 25% loss in the range of motion of the joint compared to the contralateral side, especially in abduction and external rotation, or on physical examination or positivity of at least one of the impingement tests including jobb, lift off, ERLS, speed, yergeson, O Brien's test, dropparm tests or popeye signs. \*Diagnose of partial supraspinatus with ultrasound or MR -

Exclusion Criteria:

\* Patients with incomplete skin integrity, hyperemia, signs of infection or tattoos

\*Patients with suspected full-thickness tear

\*History of rheumatic disease (rheumatoidarthritis, osteoarthritis, PMR)

\*Patients with accompanying shoulder pathology such as calcifictendinitis

\*History of malignancy

\*Surgery, manipulation, mobilization, arthroscopy performed on the affected shoulder

\*Steroid, local anesthetic, hyaluronic acid injection, cnesiotaping or neural therapy in the affected shoulder in the last 3 months

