## 5. STUDY DESIGN & METHOD

#### STUDY DESIGN

90 patients aged 20-60 years who were diagnosed with partial supraspinatus tear and met the inclusion criteria of the study will be included in the study. Patients will be randomized into three groups: 30 patients in the first group who have 5 sessions of high-intensity laser, 30 patients in the second group who have 10 sessions of high-intensity laser, and 30 patients in the third group control group who have only exercises. It was planned to give 5 sessions of laser+exercise every other day to the the first group, 10 sessions of laser+exercise every other day to the second group, and only exercise program three days in a week to the control group. All groups will be evaluated with joint range of motion (ROM) (measurements including abduction, adduction, flexion, extension, internal and external rotation by goniometer according to neutral 0 position), visual analog scale (VAS), shoulder pain dissability index, quickdash, constant score at 0th month, 1st month, 3rd and 6th months.

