#### **DETAILS of METHOD**

Patients in the laser group will be given hiltherapy (high-intensity laser) with the HIRO 3 device every other day. One session of laser therapy application consists of 3 phases: the beginning, the middle and the ending phase. The initial phases are fast scanning and the ending phase is slow scanning. A total of 2000 J will be applied to the rotatorcuff muscles, the upper part of the trapezius muscle, the deltoid muscle and the pectoralis major muscle, 1000 J in the rapid scan phase and 1000 J in the finishing phase. In the middle phase, 50 J will be applied for the trigger point (hard intramuscular points that cause referred pain) in each muscle and a maximum of 500 J in total. The total dose prescribed for patients in one session will be 2500 J. Each phase will be 15 minutes on average and the session will last for 45 minutes in total. The laser probe will be applied with 90 degrees. During the application, the practitioner and the patient will have protective glasses.

Patients in the laser group will be given hiltherapy (high-intensity laser) with the HIRO 3 device every other day. One session of laser therapy application consists of 3 phases: the beginning, the middle and the ending phase. The initial phases are fast scanning and the ending phase is slow scanning. A total of 2000 J will be applied to the rotatorcuff muscles, the upper part of the trapezius muscle, the deltoid muscle and the pectoralis major muscle, 1000 J in the rapid scan phase and 1000 J in the finishing phase. In the middle phase, 50 J will be applied for the trigger point (hard intramuscular points that cause referred pain) in each muscle and a maximum of 500 J in total. The total dose prescribed for patients in one session will be 2500 J. Each phase will be 15 minutes on average and the session will last for 45 minutes in total. The laser probe will be applied with 90 degrees. During the application, the practitioner and the patient will have protective glasses.

30 patients will be included to control group. They will take only exercise program three times in a week. **Description of Transactions on Working Days & Visits** 

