## **10. STATISTICAL PROCEDURES**

Sample Size

Sample size calculation was made using G\*POWER 3.1.9 program. Using the findings of a similar study conducted before (6), it was predicted that a high level of effect size would be obtained between the groups (f=0.40) for the SPADI score of  $22\pm1.2$  for the 6th month before and after the treatment and  $41.4\pm2.6$  for the control group (f=0.40), 90% power, and type 1 error level: 5%, it is aimed to reach at least 84 people in total, and at least 90 people considering that there may be losses in the follow-up.

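### The pre-entry washout leaves out laser, the one treatment that defines the three arms

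*Combined protocol and SAP*

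**What the plan says.** Two items in the section 4 exclusion list concern earlier treatment of the affected shoulder. One has a time window: "Steroid, local anesthetic, hyaluronic acid injection, cnesiotaping or neural therapy in the affected shoulder in the last 3 months". The other has none: "Surgery, manipulation, mobilization, arthroscopy performed on the affected shoulder". Neither names laser. The remaining entry exclusions concern skin, disease and neurological conditions, and the later paragraph on exclusion from the study deals with attendance after entry.

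On who comes in, section 4 states "Volunteers will be included in the study among the patients who applied to the FTR outpatient clinic" and requires "Patients with VAS>4 pain in the shoulder for at least 3 months".

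On what separates the arms, the Study Design text gives the first group 5 sessions of laser plus exercise, and then "10 sessions of laser+exercise every other day to the second group, and only exercise program three days in a week to the control group". The method details repeat for controls: "They will take only exercise program three times in a week". Comparing 5 with 10 sessions is the stated secondary purpose.

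The sample size paragraph in section 10 refers to SPADI at the 6th month, and there "it was predicted that a high level of effect size would be obtained between the groups (f=0.40"). It adds 90% power, a 5% type 1 error, at least 84 people, and 90 to allow for losses.

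The visit description names demographic information as a baseline item. Prior treatment is not named there, as an allocation factor, or in the analysis methods.

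**The concern.** The plan washes out several recent local treatments, taping among them, but not the treatment under test. Exercise is common to all three arms, so laser exposure is the only intended contrast. A control patient who had laser to the same shoulder shortly before entry meets the criteria as written. So does a patient allocated to 5 sessions who has just completed a course elsewhere. For such patients the labels for no laser, 5 sessions and 10 sessions describe what the trial gave, not their recent exposure.

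The plan's own premise makes this relevant. Sizing on a large difference at month 6 supposes that laser acts for months, so laser given in the weeks before entry cannot be dismissed as spent. Recruiting from an outpatient clinic patients with at least 3 months of pain makes earlier conservative treatment possible.

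At stake is the clarity of the laser-control comparison and of the 5-versus-10 comparison. If prior laser is not asked about, any dilution can be neither measured nor adjusted for afterwards, and a null result would be harder to interpret.

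**Working it through.** **Inputs from the documents.** Three groups, f=0.40, two-sided 5% type 1 error, 90% power, 84 people needed and 90 planned (section 10); equal groups of 30 (Study Design).

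**Step 1: reproduce the plan's figure.** One-way ANOVA omnibus F test with k=3 groups, degrees of freedom (2, N−3) and noncentrality λ = N·f².

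- N=81: power 0.895, short of 90%.
- N=84: λ = 84 × 0.16 = 13.44, degrees of freedom (2, 81), power 0.907.

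So 84 is the smallest total divisible by three that reaches 90%, and the plan's figure reproduces. With all 90 retained, power is 0.926. A washout for laser does not alter this calculation.

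**Step 2: worst-case illustration.** Let p be the share of patients in each arm with recent laser. The documents give no value, so 10%, 20% and 30% are assumptions. Suppose these patients have the same expected outcome in whichever arm they are placed, so they contribute no laser effect. Differences between arm means then shrink by the factor (1−p). Holding the within-arm SD fixed, f = 0.40 × (1−p).

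| p (assumed) | f | λ at N=84 | Power, N=84 | Power, N=90 |
|---|---|---|---|---|
| 0% | 0.40 | 84 × 0.1600 = 13.44 | 0.907 | 0.926 |
| 10% | 0.36 | 84 × 0.1296 = 10.89 | 0.834 | 0.861 |
| 20% | 0.32 | 84 × 0.1024 = 8.60 | 0.734 | 0.766 |
| 30% | 0.28 | 84 × 0.0784 = 6.59 | 0.610 | 0.643 |

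**Step 3: the other end of the range.** Suppose instead that prior sessions simply add to trial sessions, that response is roughly linear in their number, and that prior sessions are spread evenly over the arms. Every arm mean then shifts by the same amount and the differences are unchanged. The loss under this reading comes only from extra between-patient variance. For any given p, the effect on the expected differences therefore runs from none to the figures in the table, and the documents do not say where in that range it lies.

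**Step 4: what the figures do not cover.** Turning f=0.40 into a laser-control difference needs a pattern of means. If both laser arms have the same mean, d = 3f/√2 = 1.2/1.414 = 0.85 SD. Under that pattern the 5-versus-10 difference is already zero. The calculation therefore gives no size for the secondary comparison.

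**The case against.** Four objections carry weight.

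- **The pain criterion limits carry-over.** Read literally, pain above 4 throughout at least 3 months leaves out a patient who was still doing well after laser given a month earlier. This stands as a limit on carry-over, but not as a complete safeguard: partial benefit is compatible with a score above 4, and the patient remains eligible.
- **The criterion acts before allocation.** A reader might infer that the laser arms fill up with patients who have already failed laser and that the comparison is therefore biased. The documents do not support this. Such patients enter the control arm equally, and sound randomization balances them in expectation. That balance does depend on the allocation being sound: the Randomization section describes allocation by order of application, while section 10 names GraphPad.
- **Exercise is different.** A reader might extend the point to a recent physiotherapy or exercise course. Every arm receives exercise, so a past course cannot blur the session labels; it can only affect baseline, room to improve and variance. Manipulation and mobilization are already excluded. Barring recent physiotherapy in a trial that recruits from a physical therapy clinic would be a real trade-off.
- **The size is assumed.** Neither the shares nor the absence of any further effect comes from the documents. This stands in full.

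It is also fair to say that the plan gives no reason for its washout items, and that it requires a case report form without listing its fields. Prior laser is therefore not named as a recorded item, but it cannot be shown that the form omits it.

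**Conclusion.** The omission is real and limited to laser. Nothing in the entry criteria bars or time-limits recent laser to the affected shoulder, although the arms are defined by laser sessions and the sizing presumes an effect at month 6. Given sound randomization, the result is dilution and noise.

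The fall in omnibus power from 91% to 83%, 73% or 61% at N=84 is a worst-case illustration. It rests on assumed shares of 10%, 20% or 30%, spread evenly over the arms, no further laser effect in those patients, and an unchanged SD. It is not an estimate of what will happen. It does not show that the planned 84 is wrong, and it puts no figure on the 5-versus-10 comparison. The case for acting is that the gap concerns the defining treatment and is cheap to close.

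**What to change.** Add 'laser therapy of any type to the affected shoulder' to the existing time-limited exclusion item in section 4. The look-back should be at least the 3 months already used there. Whether a longer period is warranted, given the month-6 difference assumed in the sizing, is for the investigators to decide and justify.

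Ask about prior laser at screening and record the answer on the case report form. Record prior physiotherapy or exercise at baseline as a descriptive item, without making it an exclusion.

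The cost is one phrase in the exclusion list and a few entries on the form. The calculated sample size stays at 84. The downside is that a few clinic patients become ineligible or are delayed, so recruitment is slightly slower; how many cannot be said from the documents.

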# Protocol name/ version number /date: Efficacy of high-intensity laser therapy in patients with partial supraspinatus tears Versivon no: 02 - Tarih: 02.12.2020

\*Reflex sympathetic dystrophy, neurodeficit in the affected extremity

\*Diabetes patients or any Patients who cannot feel the burning pain due to a peripheral neuropathy or sensory defect

\*Patients with epilepsy

**Exclusion Criteria and Practices in this Case** 

Patients will be excluded from the study if they do not attend follow-up and laser sessions regularly.

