6. COLLECTION OF STUDY DATA

#### Data Recording/ Case Report Forms

A Case Report Form will be completed for each registered patient and signed by the responsible investigator or an authorized representative of the study staff. This also applies to enrollments for patients who did not complete the study (even during pre-randomisation screening, if a case report form was prepared). If a patient withdraws from the study, the reason for this will be recorded on the Case report form. If a patient is withdrawn from the study due to a treatment-limiting adverse event, every effort will be made to clearly document the outcome. All forms must be typewritten or filled with indelible ink and be legible. Errors can be crossed out, but errors cannot be erased; correction is entered and the change is initialed and dated by the researcher or his authorized representative. The investigator will ensure that the data reported to the sponsor in case report forms and all required reports are correct, complete, legible and processed in a timely manner. The researcher is responsible for the accuracy of the data transferred on the forms and will sign these forms to show their compatibility with the recorded data.

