#### Statistical & Analytical Methods

The data will be analyzed with the SPSS 18.0 package program. GraphPad for Windows will be used in the randomization process. Continuous variables will be presented as mean and standard deviation or median (25p-75p). Categorical variables will be presented as percentages. The conformity of the data to the normal distribution will be evaluated with the Shapiro Wilk test. Analysis of variance (ANOVA) and split-mixed ANOVA will be used in the analysis of within-group changes and in repeated measures of significance between the differences between groups. Tukey and Games Howell tests will be used in post-hoc tests.

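### Irregular attenders are removed after randomisation, with no threshold and no as-randomised analysis set; if missed laser sessions alone suffice, only the laser arms can lose patients that way

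*Combined protocol and SAP*

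**What the plan says.** The last part of section 4, on exclusion and what is done in that case, reads: "Patients will be excluded from the study if they do not attend follow-up and laser sessions regularly". No number or proportion of sessions or visits is attached to the final word. The sentence also leaves open whether failing one of the two elements is enough or both must fail.

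The arms differ in what there is to attend. Section 5 (Study Design) plans "5 sessions of laser+exercise every other day to the the first group" and "10 sessions of laser+exercise every other day to the second group, and only exercise program three days in a week to the control group". Details of Method repeats for the controls: "They will take only exercise program three times in a week". All three arms exercise, but no attendance rule covers exercise. Section 5 also states that there is no blinding.

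The passages that might limit the effect of the rule are these:

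- Section 5 schedules all groups for assessment at months 0, 1, 3 and 6.
- Section 6 requires a case report form for every registered patient, including those who do not complete, and adds: "If a patient withdraws from the study, the reason for this will be recorded on the Case report form".
- Section 10 (Sample Size) aims for "at least 84 people in total, and at least 90 people considering that there may be losses in the follow-up".
- Section 10 (Statistical & Analytical Methods) says "Analysis of variance (ANOVA) and split-mixed ANOVA will be used in the analysis of within-group changes". It names no analysis set and no rule for missing data.

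**The concern.** Randomisation makes the arms comparable as allocated. Removing patients for something that happens after allocation can undo that, and here the removal is from the study, not only from treatment.

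If failing either element is enough, the laser element can be failed only in the two laser arms, while the follow-up element applies to all three. Exposure to the rule also differs within laser, with 5 sessions against 10, so the secondary comparison is touched as well. If both elements must fail, the laser-only route largely disappears, but irregular attenders are still removed. In either case staff who know the arm decide what counts as regular.

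The primary purpose is to demonstrate efficacy. If excluded patients differ in outcome and are excluded at different rates by arm, the comparison is biased when laser has no effect. Some of the loss could not be repaired later: a patient removed during the laser course would have no post-baseline score.

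**Working it through.** **The plan's own figure.** Inputs from section 10: three groups, f = 0.40, 5% type I error, 90% power. For the one-way ANOVA F test with noncentrality N × f² and degrees of freedom 2 and N − 3:

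- N = 81: noncentrality 12.96, power 89.5%
- N = 84: noncentrality 13.44, power 90.7%
- N = 90: noncentrality 14.40, power 92.6%

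So 84 reproduces as the smallest multiple of three reaching 90%. The step to 90 allows for 6 losses, 6/90 = 6.7%.

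**When removal could occur.** With laser every other day, session k falls on day 2k − 1. Session 5 is on day 9 and session 10 on day 19. Both precede the month 1 assessment.

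**Bias with no true effect.** Assumptions, none from the documents: 30 per arm, full-arm SD of 1, and excluded patients differing from retained ones by a gap g (positive means worse). The retained mean in an arm shifts by exclusion rate × g, so

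bias = (laser-arm exclusion rate − control exclusion rate) × g, where positive favours laser.

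For example, 4 of 30 excluded in the 10-session arm and 0 of 30 in control with g = 1.0 gives (4/30 − 0) × 1.0 = 0.133 SD. The type I errors below are from simulation of a one-way ANOVA on retained patients at one time point (200,000 runs per case).

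| Excluded: 5-session / 10-session / control | 10-session bias (SD), g = 0.5 / 1.0 | Omnibus type I error, g = 0.5 / 1.0 |
|---|---|---|
| 3/3/0 | 0.050 / 0.100 | 5.3% / 6.5% |
| 2/4/0 | 0.067 / 0.133 | 5.4% / 6.9% |
| 2/3/1 | 0.033 / 0.067 | 5.1% / 5.5% |
| 2/2/2 | 0 / 0 | 5.1% / 5.1% |
| 1/1/4 | −0.050 / −0.100 | 5.3% / 6.3% |
| 3/6/0 (nine exclusions) | 0.100 / 0.200 | 6.0% / 9.3% |

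If g = 0 the bias is zero in every row. If excluded patients do 0.5 SD better, the first three rows change sign: −0.03 to −0.07 SD.

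The planned split-mixed ANOVA behaves similarly. With four visits, the gap present from month 1, and equal correlation of 0.3, 0.5 or 0.7 (20,000 runs per case), the first three splits give type I error of 5.1% to 7.0% for group and 4.9% to 7.4% for group by time.

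**Scale.** If the laser arms are equal, f = 0.40 means a laser-versus-control difference of 0.40/√(2/9) = 0.849 SD. Then 0.033/0.849 = 4% and 0.133/0.849 = 16% of the design effect.

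**What the missing threshold decides.** Assume each session is missed independently with probability 5%:

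- No missed session allowed: 1 − 0.95⁵ = 22.6% excluded with 5 sessions, and 1 − 0.95¹⁰ = 40.1% with 10.
- At least 80% attended: P(2 or more of 5 missed) = 2.3%, and P(3 or more of 10 missed) = 1.2%.

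The choice of threshold changes the number removed by an order of magnitude, and changes which laser arm loses more.

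**The case against.** The strongest case is about severity. Within the six-patient allowance the bias is at most 0.13 SD and the type I error at most 6.9% at a single time point, against a design effect of about 0.85 SD. The upper end needs every exclusion in the laser arms and a 1.0 SD gap, and the documents support neither. The 9.3% case needs nine exclusions, more than the allowance. This stands as a statement about size. It does not remove the defect: six is a planning figure and not a cap, and the objection to the rule is one of principle.

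The one-sided loss rests on one reading of an ambiguous sentence. That is correct, and the point is conditional for that reason. The removal rule without a threshold or analysis set does not depend on that reading.

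The plan does document non-completers and schedules all groups for every assessment, and it does not say that data already collected are discarded. A patient removed after month 1 might therefore still contribute. This is fair, but none of these passages overrides the exclusion or requires follow-up to continue.

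The threshold figures assume independent sessions. Clustering of missed sessions within patients would lower the 22.6% and 40.1%. They show only that the threshold matters.

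Finally, keeping non-attenders in the analysis has a price in power, which is set out with the fix.

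**Conclusion.** The concern holds and must be fixed before the trial is run or analysed. As written, the protocol removes randomised patients for behaviour seen only after allocation, by an undefined criterion, in an unblinded trial, and nothing in the plan keeps them in follow-up or analyses them as randomised.

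Size and direction cannot be derived from the documents. In the three unequal splits of six exclusions with more in the laser arms, and with excluded patients 0.5 to 1.0 SD worse, the 10-session arm is favoured by 0.03 to 0.13 SD. The bias vanishes if exclusions are equal across arms or unrelated to outcome. It reverses if excluded patients do better or if controls are excluded more often. The severity rests on the loss of the randomised comparison, and on outcomes that no analysis could restore once a patient is removed before month 1. It does not rest on these illustrative figures.

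**What to change.** Remove attendance as a ground for exclusion from the study and from the analysis. In its place, state:

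*All randomised patients are assessed at months 1, 3 and 6 whatever their attendance, and are analysed in the group to which they were randomised, using all available visits. Attendance is reported by arm. Any per-protocol analysis is a sensitivity analysis only, with numeric attendance thresholds fixed in advance for laser sessions in the laser arms and one common exercise criterion in all three arms.*

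A linear mixed model is one way to use all available visits. The change concerns follow-up and analysis only, not treatment decisions.

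The cost is protocol and SAP wording, contacting non-attenders for visits already scheduled, and an attendance record. The documents do not say whether exercise is supervised, so a patient diary may be needed in all arms.

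The downside is dilution by non-adherence. Take the pessimistic assumption that non-attenders gain nothing from laser, so that f = 0.40 × (1 − non-attendance). At N = 90, non-attendance of 5%, 10% or 20% then gives f = 0.38, 0.36 or 0.32 and power of about 89.8%, 86.1% or 76.6%. Partial attenders may benefit, so the true loss could be smaller. The change itself adds no patients, but the sponsor should check the expected attendance against these figures. They are a caveat, not a reason to keep the exclusion.
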